##### **Removal by Qualified Investigator:**

Participant discontinuation should be considered at the discretion of the Qualified Investigator. The circumstances of any discontinuation must be documented in detail in the participant file and final report. If possible, the evaluations planned for the end of study will be carried out at the time when the participant is withdrawn from the study. A participant leaving the study prematurely will be replaced by another if required to ensure 30 participants complete the study. It is understood by all concerned that an excessive rate of withdrawals can render the study uninterpretable; therefore, unnecessary withdrawal of participants should be avoided.

Criteria for removal of participants from the study will include:

#### **Clinical reasons**

A participant may be withdrawn from the study if, in the opinion of the Qualified Investigator, it is not in the participant's best interest to continue. Any participant who experiences a serious adverse event (SAE) may be withdrawn from the trial at the discretion of the Qualified Investigator. A participant will also be withdrawn due to adverse events causing clinically significant illness or the need for prohibited medication(s) during the trial. Any female participant who becomes pregnant during the course of the trial will be withdrawn.

#### **Protocol violation**

Any participant found to have entered this study in violation of the protocol will be discontinued from the study at the discretion of the Qualified Investigator. This will include any participant found to have been inappropriately enrolled (did not meet eligibility criteria). Participant non-compliance includes not showing up for study visits or refusing to undergo study visit procedures. Participants who are found to be taking prohibited medications or supplements without the knowledge of the Qualified Investigator will also be withdrawn. Any major protocol deviations (i.e., those that increase the risk to participants and/or compromise the integrity of the study or its results) will result in participant discontinuation.

### **5 INVESTIGATIONAL PRODUCT**

#### **5.1 Manufacturing and Storage**

The investigational product will be provided to KGK by the Sponsor. The investigational product will be carefully stored at the study site in a lockable, limited access area, accessible only to study team personnel in compliance with pertinent regulations. Only authorized persons will have access to the investigational product. The products will be stored at room temperature and will not be exposed to direct sunlight or heat. The investigational products will be kept in a locked investigational product storage room at KGK Synergize Inc. on receipt. An accountability log will be kept for the investigational products.

All unused investigational product will be returned to the study sponsor by KGK (at the sponsor's expense) or destroyed on receipt of written confirmation from the sponsor at study closeout (within one month of last participant visit).

## 5.2 Labeling and Coding

The investigational product will be labeled per the requirements of ICH-GCP guidelines and applicable local regulatory guidelines. The investigational product will be randomized and coded by an un-blinded person at KGK who is not involved in data collection or analysis.

## 5.3 Investigational Products

### 5.3.1 Gummy Product:

Sponsor Reference No.	Dietary Ingredient	Amount per serving per label claim	Use Instructions
4796-81A	Vitamin C	240 mg / two gummies	Chew thoroughly before swallowing

Other ingredients: *Sodium Citrate, Natural Flavor, Glucose Syrup, Rose Hips, Sucrose, Gelatin, Citric Acid, Color (annatto extract), Fumaric Acid, Lactic Acid, Sodium Citrate.*

### 5.3.2 Comparator Product:

Sponsor Reference No.	Dietary Ingredient	Amount per serving per label claim	Use Instructions
4796-81B	Vitamin C	500 mg / one caplet	Take with water

Other ingredients: *cellulose gel, hydroxypropyl Methylcellulose, Rose Hips, Croscarmellose Sodium, Stearic Acid, Silicon Dioxide, Magnesium Stearate.*

## 5.5 Dosing Directions

A dose of 1000 mg vitamin C will be used in this study based on a recently published article in which a threshold of plasma ascorbic acid level of 37  $\mu$ M was observed post dosing (8). Participants will consume the investigational products with 250 mL water in front of the clinical coordinator. The investigational products will be provided based on analytical results in the number of gummy or caplet in a quantity as close as possible between 975 and 1025 mg/dose ( $1000 \text{ mg} \pm 2.5\%$ ). To ensure examiner blinding clinic coordinators not involved in collecting study data will dispense investigational products to the participants. Participants will be instructed to chew the gummies thoroughly before swallow. A total of 250 mL of water is to be consumed together with the study product. The time of investigational product intake will be recorded. Water will be permitted ad libitum starting 1-hour after dosing and the clinic coordinator will encourage the participants to drink water throughout the day. Participants will be allowed to sit / rest yet will not be permitted to recline for 2 hours after dosing.

## 5.6 Randomization

A randomization schedule will be created and provided to the Investigator indicating the order of randomization (Appendix 5). Each participant will be assigned a randomization code according to the order of the randomization list generated using [www.randomization.com](http://www.randomization.com). Enrolled participants will be randomized to the different study arms at the Baseline Visit.

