## 5.7 Un-blinding and Allocation Concealment

This study is single blinded (examiner only) due to the obvious difference in product form (gummy vs. caplet). Un-blinding should not occur except in the case of emergency situations. If a serious adverse event occurs, for which the identity of the investigational product administered is necessary to manage the participant's condition, the supplement received by the participant will be un-blinded and the investigational product identified. Concealment of the allocation of supplement will be employed using opaque sealed envelopes, each labeled with a randomization number. Each envelope will contain information regarding the supplement associated with each randomization number. These envelopes will be readily available for the investigator to open if it becomes necessary to know which product a participant is taking for the sake of the participant health care. The sponsor must be notified of any un-blinding within 24 hours. Details of participants who are un-blinded during the study will be included in the Final Report.

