## **6.3 Visit 2 – Baseline: Clinic Day 1 (Test Period 1, 8h In-Clinic Day)**

Eligible participants will return to the clinic after fasting for 12 hours (only water is allowed) for baseline assessments.

Baseline assessments include:

- Reviewing of concomitant therapies and current health status
- Physical exam
- Assessing of inclusion and exclusion criteria
- Collecting 7-day food record and reviewing dietary compliance
- Randomizing eligible participants

- Recording weight and BMI
- Recording seated resting blood pressure and heart rate
- Blood collection (plasma and WBC) for pre-dose baseline (0h) analysis of L-ascorbic acid
- Pre-dose urine collection (baseline 0h) and total urine volume will be recorded and a sample for L-ascorbic acid analysis will be retained
- Following randomization and collection of pre-dose samples, Investigational product administration with 250 mL of room temperature water and recording of consumption time. Participants who receive the gummies will be instructed to chew gummies thoroughly before swallowing. Water will be permitted ad libitum 1-hour after dosing.
- Participants will be instructed to avoid reclining for 2 hours after dosing.
- Blood collection (plasma and WBC) for post-dose analysis of L-ascorbic acid at 30min, 1h, 2h, 3h, 4h, 5h, 6h, 8h, 10h and 12h post-dose
- Urine collection between 0-2h post-dose and total volume will be recorded.
- Sample of 0-2h post dose urine will be retained for L-ascorbic acid analysis
- Urine collection between 2-4h post-dose and total volume will be recorded.
- Sample of 2-4h post dose urine will be retained for L-ascorbic acid analysis
- Urine collection between 4-8h post-dose and total volume will be recorded
- Sample of 4-8h post dose urine will be retained for L-ascorbic acid analysis
- Urine collection between 8-12h post-dose and total volume will be recorded
- Sample of 8-12h post dose urine will be retained for L-ascorbic acid analysis
- Recording of adverse events

Standardized meals devoid of vitamin C containing products will be provided to participants in the clinic (Refer to appendix 4). The following meals will be provided at the clinic: Breakfast after the 2h blood sampling, lunch after the 5h blood sampling, and supper between the 6h and 12h sampling. All food items and quantities consumed will be recorded by clinic staff for each individual participant.

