## 6.8.3 Compliance

Investigational product compliance calculations are not necessary in this study as the study supplements will be administered in the clinic. Participants will be asked to consume the supplements in front of the clinical coordinator. Compliance to the dietary restrictions of the protocol will be assessed using the food records completed by the participant. In the event that a participant consumes foods and/or beverages with high vitamin C content (see Appendix 2), the Qualified Investigator will determine the significance and if the participant should continue in the study.

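### Section 5.6 gives the Investigator the ordered, lettered Appendix 5 schedule, so the concealment and examiner blinding described in 5.7 are not assured for that person

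*Combined protocol and SAP*

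**What the plan says.** Section 5.6: "A randomization schedule will be created and provided to the Investigator indicating the order of randomization (Appendix 5". It adds that codes are assigned in list order and that randomization takes place at the Baseline Visit.

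Appendix 5 is a combined randomization schedule and dispensing log, one list per sex. Each row has a randomization number, a space for the participant ID, a Week 1 letter, a Week 2 letter, and dispensing dates and initials. Two numbers at the end of each list are marked as not to be used.

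Section 5.7 describes a single-blind (examiner-only) study and says: "Concealment of the allocation of supplement will be employed using opaque sealed envelopes, each labeled with a randomization number". On access it says: "These envelopes will be readily available for the investigator to open if it becomes necessary to know which product a participant is taking". Any un-blinding must be notified to the sponsor within 24 hours, and un-blinded participants are described in the Final Report.

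Two other sections protect the blind. Section 5.2: "The investigational product will be randomized and coded by an un-blinded person at KGK who is not involved in data collection or analysis". Section 5.5: "To ensure examiner blinding clinic coordinators not involved in collecting study data will dispense investigational products to the participants".

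**The concern.** A sealed envelope conceals little from someone who holds the open list in assignment order. Sections 5.2, 5.5 and 5.7 keep allocation away from people who make judgements about participants. Section 5.6 then hands the schedule to the Investigator, and no text masks or restricts that copy.

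Reading Appendix 5 also bypasses the control in 5.7. No envelope is opened, so nothing prompts the notice to the sponsor or the entry in the Final Report.

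At stake are judgements, not measurements:

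- **Eligibility.** Visit 2, where participants are randomized, includes "Assessing of inclusion and exclusion criteria" (6.3).
- **Adverse event causality.** This is decided by the Qualified Investigator (7.1.1). Adverse events are tabulated by product and their causality is reported (8.3.2).
- **Discontinuation and continuation.** Section 4.4: "Participant discontinuation should be considered at the discretion of the Qualified Investigator". After a dietary breach, "the Qualified Investigator will determine the significance and if the participant should continue in the study" (6.8.3). Withdrawal removes a participant from the Per Protocol (PP) set, which requires completion of all visits (8.2), and can lead to replacement (4.4, 8.3.1).

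**Working it through.** **Inputs.** Section 3 (36 randomized, 18 per sequence), Appendix 5 (the two lists), 5.3.1 and 5.3.2 (reference numbers), and 5.2, 5.5, 5.6 and 5.7 (who holds what).

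**1. Reproduce the plan's figure.** Week 1 letters in list order, first 18 rows of each list:

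- Males: BAABABBABABAAABBAB, which is 9 A-first and 9 B-first (7515 and 7507 unused).
- Females: BABABABAABABABABAB, which is 9 A-first and 9 B-first (7522 and 7536 unused).

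Total: 9 + 9 = 18 A-first and 9 + 9 = 18 B-first, or 36. This matches the 18/18 in Section 3, so Appendix 5 is the complete allocation list and not a specimen.

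**2. How much information is printed.** Week 2 is always the other letter, so each row carries one two-way fact. The list therefore holds 36 facts. Counting 36 × 2 = 72 letters would count each fact twice.

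**3. From letters to products.** Appendix 5 gives no key. There are two possible keys: A is the gummy, or A is the caplet. Two routes lead to the key:

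- The only A/B product labels in the protocol are 4796-81A for the gummy (5.3.1) and 4796-81B for the caplet (5.3.2). If the letters follow these suffixes, all 36 sequences can be read before enrolment.
- If the suffixes are ignored, one known product in one period for one listed participant rules out one of the two keys. That reveals the other 36 − 1 = 35 sequences. The source could be one opened emergency envelope or one remark by a participant, since participants are not blinded (5.7).

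**4. From rows to people.** Codes are assigned in list order and the lists are separate by sex. The next free row is therefore the next participant of that sex, and the ID is then written on the same log.

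**5. The sections side by side.**

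| Section | Who | Access to allocation |
|---|---|---|
| 5.2 | Un-blinded coder | Full, by design |
| 5.5 | Dispensing coordinators who collect no data | Handle the product, by design |
| 5.6 | Investigator | Ordered schedule, cited as Appendix 5, with letters |
| 5.7 | investigator | By envelope, only when care requires it |

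The last two rows cannot both describe a blinded Investigator.

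**The case against.** The strongest case on the other side has five parts.

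- **Appendix 5 is also the dispensing log.** The letters serve the coordinators in 5.5, and the wording of 5.6 could mean the order of numbers only. The dispensing use stands, and it is why the letters should stay on the coordinators' copy. It does not explain why 5.6 cites that same appendix as what the Investigator receives.
- **The key is inferred.** This stands. The site's un-blinded person codes the product, whereas 81A and 81B are the sponsor's reference numbers. A reader might infer that the Investigator already knows all 36 product sequences. The documents do not support that: they show letters, a matching pair of suffixes, and a code that one disclosure would break.
- **A participant's remark reveals that participant's own two periods even without a list.** This is true. The list adds the other 35 sequences.
- **Roles are undefined.** No section names the Investigator as an examiner, 6.3 does not say who assesses eligibility, and the 5.6 Investigator is not said to be the Qualified Investigator. This stands, and it makes every listed exposure conditional, eligibility included.
- **The consequence is small.** Everyone is scheduled to take both products, so foreknowledge at enrolment concerns sequence only. Samples are coded and the analysts do not know the product (6.9). Cmax is tested separately for each product against 37 µM (8.3), adverse events are summarised descriptively (8.3.2), and the study is called a pilot (8.1). This also stands, and it limits the weight of the point without removing the contradiction.

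**Conclusion.** The contradiction is in the current text. Section 5.6 with Appendix 5 gives the Investigator an ordered, lettered list for all 36 usable numbers, while 5.7 treats the investigator as blind until an envelope is opened. Allocation concealment and examiner blinding are therefore not assured for that person.

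The size is 36 disclosed sequences in letters. All 36 are readable if the letters follow the product suffixes; otherwise 35 more become readable once one participant's product is known. This counts disclosure and does not measure bias.

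The effect on judgements is conditional. If the 5.6 Investigator is the Qualified Investigator, causality and discontinuation or continuation are exposed, the last of these with an effect on the PP set. If that person assesses Visit 2 eligibility, that is exposed too. The documents settle neither.

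A reader might also infer that the Cmax result is biased or that data-collecting staff hold the list. Neither is supported. Laboratory blinding is unaffected, any effect on the per-product Cmax test is likely negligible, and no section gives the list to data-collecting staff. Participants' own adverse event reports are open-label in any case; only staff judgement of them is in question.

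The change is worth making because it restores a property that the plan itself claims.

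**What to change.** 1. Change 5.6 so that the Investigator receives only the order of randomization numbers, without the Week 1 and Week 2 letters.
2. State that the lettered Appendix 5 schedule and dispensing log is held only by the un-blinded coder (5.2) and the dispensing coordinators who collect no study data (5.5). Take the lettered list out of the protocol given to blinded staff.
3. If blinded staff have already received the list, generate a new one.
4. Keep the sealed envelopes for emergency un-blinding.
5. In 5.7, state who is blinded and whether the 5.6 Investigator is the Qualified Investigator.

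The cost is a short amendment, which may need IRB and Health Canada review (6.11), plus a new list and new envelopes if the current list has been disclosed. No new staff are needed, since both un-blinded roles are already planned. Re-lettering the products is not needed once blinded staff no longer see the letters.

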## 5.7 Un-blinding and Allocation Concealment

This study is single blinded (examiner only) due to the obvious difference in product form (gummy vs. caplet). Un-blinding should not occur except in the case of emergency situations. If a serious adverse event occurs, for which the identity of the investigational product administered is necessary to manage the participant's condition, the supplement received by the participant will be un-blinded and the investigational product identified. Concealment of the allocation of supplement will be employed using opaque sealed envelopes, each labeled with a randomization number. Each envelope will contain information regarding the supplement associated with each randomization number. These envelopes will be readily available for the investigator to open if it becomes necessary to know which product a participant is taking for the sake of the participant health care. The sponsor must be notified of any un-blinding within 24 hours. Details of participants who are un-blinded during the study will be included in the Final Report.

# 6 STUDY ASSESSMENTS

See Appendix 1 for the schedule of assessments and procedures, and Appendix 1a for time points for blood and urine sampling:

- Table 1A: A total of twelve (12) time points for blood sampling including baseline prior to dosing at 0h, and 0.5, 1, 2, 3, 4, 5, 6, 8, 10, 12 and 24 h post dosing for ascorbic acid analysis.
- Table 1B: A total of four time points for blood safety parameters.
- Table 1C: A total of six time points for urine ascorbic acid.

### 6.1 Visit 1 – Screening (Day -28 to Day -8)

At screening, a volunteer Informed Consent Form will be given to the potential participant. The volunteer will read the information carefully and will be given the opportunity to seek more information if needed. The volunteer will also be provided with the option of taking the consent form home to review prior to making his or her decision. If agreeable, the volunteer will sign the consent form and receive a duplicate. Once consent has been obtained, the screening visit will proceed. After the volunteer has signed the informed consent, the screening number will be assigned sequentially and entered in the Screening and Enrolment Log. Screening numbers will be allocated in the chronological order of the volunteer signing the informed consent. Participants will be provided with a list of meal items to choose from during the 8-h clinic visits.

Visit 1 assessments include:

- Reviewing of medical history, concomitant therapies, and current health status
- Urine pregnancy test for females of childbearing potential and participants that are not post-menopausal
- Recording weight, height, and BMI
- Recording seated resting blood pressure and heart rate
- Assessing inclusion and exclusion criteria
- Blood collection for the analysis of CBC, electrolytes (Na, K, Cl), HbA1c, creatinine, estimated glomerular filtration rate (eGFR), aspartateaminotransferase (AST), alanine aminotransferase (ALT), and bilirubin
- Dispensing 7-day food record and instructing on completion
- Nutrition counselling
- Instructing volunteers to maintain their current dietary habits but to refrain from consuming St. John's Wort, health supplements, foods and beverages containing vitamin C (Refer to Appendix 3), tomato juice, citrus food, and juice (orange, grapefruit, lemon, lime, orange juice, grapefruit juice and lemonade) 7 days prior to their next visit.
- Volunteers will be instructed to fast (water is allowed) for 12 hours prior to their next visit and avoid alcohol for 24 hour prior to coming to the clinic

Individuals will be counseled on foods to avoid during the washout period and on determining vitamin C content of fortified foods by reading labels. Foods and fortified foods containing less than 2.4 mg or 4% of recommended dietary intake (RDI) of vitamin C will be permitted during the washout period. They will be provided with a list of low vitamin C foods to be followed during their washout period, as well as examples of low vitamin C meal plans (Appendix 3).

## **6.2 Washout period (Day -8 to Day -1)**

Eligible volunteers will follow a recommended food plan and record their food/drink intake for the 7 days preceding the baseline visit. Volunteers will start fasting 12 hours before visit 2. The next visit will be scheduled for eligible participants immediately following the 7-day washout period.

## **6.3 Visit 2 – Baseline: Clinic Day 1 (Test Period 1, 8h In-Clinic Day)**

Eligible participants will return to the clinic after fasting for 12 hours (only water is allowed) for baseline assessments.

Baseline assessments include:

- Reviewing of concomitant therapies and current health status
- Physical exam
- Assessing of inclusion and exclusion criteria
- Collecting 7-day food record and reviewing dietary compliance
- Randomizing eligible participants

- Recording weight and BMI
- Recording seated resting blood pressure and heart rate
- Blood collection (plasma and WBC) for pre-dose baseline (0h) analysis of L-ascorbic acid
- Pre-dose urine collection (baseline 0h) and total urine volume will be recorded and a sample for L-ascorbic acid analysis will be retained
- Following randomization and collection of pre-dose samples, Investigational product administration with 250 mL of room temperature water and recording of consumption time. Participants who receive the gummies will be instructed to chew gummies thoroughly before swallowing. Water will be permitted ad libitum 1-hour after dosing.
- Participants will be instructed to avoid reclining for 2 hours after dosing.
- Blood collection (plasma and WBC) for post-dose analysis of L-ascorbic acid at 30min, 1h, 2h, 3h, 4h, 5h, 6h, 8h, 10h and 12h post-dose
- Urine collection between 0-2h post-dose and total volume will be recorded.
- Sample of 0-2h post dose urine will be retained for L-ascorbic acid analysis
- Urine collection between 2-4h post-dose and total volume will be recorded.
- Sample of 2-4h post dose urine will be retained for L-ascorbic acid analysis
- Urine collection between 4-8h post-dose and total volume will be recorded
- Sample of 4-8h post dose urine will be retained for L-ascorbic acid analysis
- Urine collection between 8-12h post-dose and total volume will be recorded
- Sample of 8-12h post dose urine will be retained for L-ascorbic acid analysis
- Recording of adverse events

Standardized meals devoid of vitamin C containing products will be provided to participants in the clinic (Refer to appendix 4). The following meals will be provided at the clinic: Breakfast after the 2h blood sampling, lunch after the 5h blood sampling, and supper between the 6h and 12h sampling. All food items and quantities consumed will be recorded by clinic staff for each individual participant.

Participants will remain in the clinic during the study visit from pre-dose until the 12h post-dose blood sampling. They will be allowed to watch television, use computers/laptops, read, talk, play video or board games, or sleep.

Prior to leaving the clinic participants will be reminded to maintain compliance and refrain from consuming St. John's Wort, other health supplements, foods and beverages containing vitamin C and high caffeine, alcohol, grapefruit and grapefruit juice. Participants will be reminded to maintain similar levels of physical activity throughout the study.

Participants will be provided with containers for the 12-24h urine collection.

Participants will be provided with study diary to record concomitant therapies and adverse events between the 12 and 24h clinic visit. Participants will also be provided with a food record to record food or beverages consumed between the 12 and 24h clinic visit. Participants will be instructed to return the completed food record and study diary to their next visit.

Participants will return the following day for their 24h assessment (Visit 3).

